9.3 POPULATIONS FOR ANALYSES

A total of 40 individuals are anticipated for the randomized portion of the trial; however, an additional 10 may be enrolled to account for dropouts.

9.4 STATISTICAL ANALYSES

9.4.1 GENERAL APPROACH

Baseline characteristics of the randomized groups will be summarized with means, standard deviations, and quartiles. Balance between groups will be assessed following the approach described by Schober (2018). Specifically, standardized differences will be calculated using Cohen's d whereby the difference in means or proportions is divided by the pooled standard deviation estimates. Any key variables (age, sex, height, weight, BMI, and surgical procedure) with an absolute standardized difference greater than $1.96 \times \sqrt{2/n} = 0.716$, where $n = 15$ is the target sample size per group (Austin (2009)), will be noted and included in a sensitivity analysis with a generalized linear model (e.g. linear regression for pain severity NRS or logistic regression for incidence rates) to obtain an estimate of the treatment effect adjusted for the imbalanced covariate(s). If key model assumptions are violated (i.e. homoscedasticity or Gaussian distribution for linear models), data transformations and/or alternative generalized linear models will be applied as appropriate. Missing data is expected to be negligible. In the event of unexpected missing data, multiple imputation by chained equations (Stef van Buuren, Karin Groothuis-Oudshoorn (2011). mice: Multivariate Imputation by Chained Equations in R. *Journal of Statistical Software*, 45(3), 1-67) will be applied to obtain estimates of treatment effects under the assumption of missing at random. The imputation model will exhaustively consider all measured baseline covariates and longitudinal observations to maximize the likelihood that the missing at random assumption is met.

9.4.2 ANALYSIS OF THE PRIMARY EFFICACY ENDPOINT(S)

The primary analytic approach will be an unadjusted two-sample Mann-Whitney U test of the median value of each participant's average daily NRS for Days 1, 2, 3, 4, and 7 (data is not collected on Days 5 and 6). If any key variables are imbalanced at baseline, a linear regression model, or appropriate generalized linear model, adjusting for those variables will be applied. The p-value and 95% confidence interval associated with the estimated group difference in average daily NRS will be provided. $P<0.05$ will be considered statistically significant for the primary outcomes.

9.4.3 ANALYSIS OF THE SECONDARY ENDPOINT(S)

Continuous endpoints will be analyzed with the same approach as the primary endpoint. Binary endpoints will be analyzed with Fisher's Exact test for two proportions, or logistic regression in the event of imbalance on key baseline variables. Ordinal endpoints will be analyzed with the Armitage trend test, or cumulative link regression model as warranted. We will test key secondary outcomes using a serial gatekeeping procedure. Nominal 95% confidence intervals will be provided for secondary analyses.

Study-wide Type I error control. We will use a serial gatekeeping procedure to control the study-wide type I error at 0.05 [Mascha EJ, Turan A: Joint hypothesis testing and gatekeeping procedures for studies with multiple endpoints. *Anesth Analg* 2012; 114: 1304-17]. For this procedure we therefore have prioritized (*a priori*) the study outcomes (**Table below**). Analysis will proceed in that order, and testing will proceed through each "gate" to the next set if and only if the outcome in the current set reaches significance. The significance level for each set will be 0.05 times a cumulative penalty for non-significant results in previous sets (i.e., a "rejection gain factor" equal to the cumulative product of the proportion of significant tests across the preceding sets). We will use the corresponding 2-tailed alpha level of 0.05 for the gatekeeping, as all sets involve 2-tailed tests. Treatment effects will also be assessed at individual time points regardless of preceding gatekeeping results, and no other adjustments will be made for testing multiplicity.

Serial gatekeeping procedure

Sets	Time frame	Required to pass to next set
------	------------	------------------------------

1: Pain intensity (median of 5 daily “average” NRS)	1 st week	Significance on this outcome
2: Cumulative opioid use (oxycodone equivalents)	1 st week	Significance on this outcome
3: BPI interference subscale	Postop Day 3	Significance on this outcome
4: Pain intensity (median of 5 daily “worst” NRS)	1 st week	Significance on this outcome
5: BPI interference subscale	Postop Day 7	Significance on this outcome
6: Cumulative awakenings due to pain	1 st week	Significance on this outcome
7: Pain intensity (“average” NRS)	Postop Day 7	Significance on this outcome
8: Pain intensity (“worst” NRS)	Postop Day 7	Significance on this outcome
9: Opioid use (oxycodone equivalents)	Postop Day 7	Significance on this outcome
10: Awakenings due to pain	Postop Day 7	Significance on this outcome
11: Opioid use (oxycodone equivalents each day)	Postop Days 1, 2, 3, 4, 8, 14	Significance on this outcome
12: Pain intensity (each daily “average” NRS)	Postop Days 1, 2, 3, 4, 8, 14	Significance on this outcome
13: Pain intensity (each daily “worst” NRS)	Postop Days 1, 2, 3, 4, 8, 14	Not applicable

9.4.4 SAFETY ANALYSES

Device-related Adverse Events. The investigators will record all device-related adverse events. These complications cannot be “ranked”, but rather the two groups will be compared descriptively on each of these possible complications.

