Randomization [**all research specific**] will be stratified by anatomic location (shoulder and foot/ankle surgery) in a 1:1 ratio and in blocks of 2. Computer-generated randomization lists will be created by the UC San Diego Investigational Drug Service and the allocation provided to the investigators *via* sequential, opaque envelopes. Pulse generators are available that are capable of either (1) passing electrical current; or (2) not passing electrical current. Importantly, these 2 modes (active and sham) are indistinguishable in appearance, and therefore investigators, participants, and all clinical staff will be masked to treatment group assignment, with the only exception being the unmasked individuals who insert the RELAY and program the stimulator.

The RELAY system with the integrated needle will be inserted adjacent to the target nerve with an in-plane approach [**same as standard-of-care**]. Dextrose 5% in water (1-20 mL) will be injected via the needle to open a space around the target nerve(s) [**research specific**], the catheter advanced [**same as standard-of-care**], and the needle subsequently withdrawn [**same as standard-of-care**].

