8.3.3.2 RELATIONSHIP TO STUDY INTERVENTION

All adverse events (AEs) must have their relationship to study intervention assessed by the clinician who examines and evaluates the participant based on temporal relationship and his/her clinical judgment. The degree of certainty about causality will be graded using the categories below. In a clinical trial, the study product must always be suspect.

- **Related** – The AE is known to occur with the study intervention, there is a reasonable possibility that the study intervention caused the AE, or there is a temporal relationship between the study intervention and event. Reasonable possibility means that there is evidence to suggest a causal relationship between the study intervention and the AE.
- **Not Related** – There is not a reasonable possibility that the administration of the study intervention caused the event, there is no temporal relationship between the study intervention and event onset, or an alternate etiology has been established.

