8.3.4 TIME PERIOD AND FREQUENCY FOR EVENT ASSESSMENT AND FOLLOW-UP

The occurrence of an adverse event (AE) or serious adverse event (SAE) may come to the attention of study personnel during hospitalization or post-discharge follow-up data-collection phone calls.

All AEs including local and systemic reactions not meeting the criteria for SAEs will be captured on the appropriate case report form (CRF). Information to be collected includes event description, time of onset, clinician's assessment of severity, relationship to study product (assessed only by those with the training and authority to make a diagnosis), and time of resolution/stabilization of the event. All AEs occurring while on study must be documented appropriately regardless of relationship. All AEs will be followed to adequate resolution.

Any medical condition that is present at the time that the participant is screened will be considered as baseline and not reported as an AE. However, if the study participant's condition deteriorates at any time during the study, it will be recorded as an AE.

Changes in the severity of an AE will be documented to allow an assessment of the duration of the event at each level of severity to be performed. AEs characterized as intermittent require documentation of onset and duration of each episode.

A study coordinator will record all reportable events with start dates occurring any time after informed consent is obtained until 7 (for non-serious AEs) or 30 days (for SAEs) after the last day of study participation. At each study visit, the investigator will inquire about the occurrence of AE/SAEs since the last visit. Events will be followed for outcome information until resolution or stabilization.

Precautions and responses to possible specific adverse events:

Infection: The perineural catheters will be inserted under sterile conditions and affixed using liquid adhesive and a sterile occlusive chlorohexidine-impregnated dressing. Phone calls to participants will include questions regarding signs and symptoms of catheter site infection. Should a catheter site become suspicious for infection, the site will be evaluated by a physician investigator. If indicated, the

catheter will be removed, the catheter tip cultured, and the subject placed on the appropriate antibiotics.

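### Section 9.4.4 compares the arms only on device-related adverse events, an undefined term, and no summary of all adverse events by randomised arm is planned

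*Combined protocol and SAP*

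**What the plan says.** Section 9.4.4 (Safety Analyses) has a single topic, device-related adverse events. It states "The investigators will record all device-related adverse events", and the sentence after it sets the comparison: "the two groups will be compared descriptively on each of these possible complications". The second sentence is the one that restricts the analysis, because the complications it refers to are the device-related ones just named. The section neither defines device-related nor refers to another section for a definition.

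Collection is wider. Section 8.3.4 says "All AEs occurring while on study must be documented appropriately regardless of relationship", with events recorded from consent "until 7 (for non-serious AEs) or 30 days (for SAEs) after the last day of study participation".

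Section 8.3.3.2 sets out the grading: "All adverse events (AEs) must have their relationship to study intervention assessed by the clinician who examines and evaluates the participant". There are two categories, Related and Not Related, and both refer to the study intervention, not to the device. One sufficient condition for Related is that "there is a temporal relationship between the study intervention and event".

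Section 8.3.5 sends a report or log of all adverse events to the IRB at annual renewal or closeout and does not mention arms. Section 3 lists no safety endpoint, and the gatekeeping table in section 9.4.3 contains none. The title and section 4.1 nevertheless give safety as an aim alongside efficacy.

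**The concern.** The sham arm has the same catheter inserted and the same local anesthetic injected as the active arm; under section 6.1.1 the intended difference is whether current is delivered. Randomisation therefore already separates the contribution of stimulation from that of the catheter, the block and the surgery. A count of all events by arm uses that separation directly and needs nobody to decide what caused an event. Selecting events by presumed cause before comparing the arms gives it up.

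This matters here because the protocol makes claims about events that a clinician could reasonably put down to something else. Section 2.2 says neuromodulation has no adverse systemic side effects, and section 2.3.2 expects fewer opioid-related effects such as nausea, vomiting and constipation. No listed endpoint measures these. If they are graded as due to oxycodone or to surgery, they drop out of the only planned safety comparison. The restriction can therefore hide a benefit of stimulation as well as a harm.

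**Working it through.** The plan gives no figure for this point, so the check is mainly a comparison of sections.

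**1. Collected against compared.** All adverse events are documented, with severity and relationship (8.3.4). With participation ending at Day 14 (section 4.4), the recording window runs to Day 14 + 7 = 21 for non-serious events and Day 14 + 30 = 44 for serious ones. Only device-related events are compared between arms (9.4.4). The full set is otherwise used only for reports to the IRB and the sponsor (8.3.5, 8.3.6, 8.4.2) and for safety oversight (10.1.6). No table of all events or all serious events by arm appears in sections 3 or 9.

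**2. What device-related could mean.** Two readings are open.
- It means events graded Related under 8.3.3.2. The comparison then depends on the clinician's causality judgement.
- It means the event types discussed in 2.3.1 and at the end of 8.3.4: infection, bleeding, dislodgement, lead migration, pain and nerve injury. No causality judgement is then needed, but nausea, falls and surgical wound problems are not on that list.

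Events of the second kind can be left out under either reading, so the gap does not depend on which one was intended.

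**3. Whether the grading rule settles the matter.** Under 8.3.3.2 timing alone makes an event Related, while an established alternative cause makes it Not Related. Nausea in a participant taking oxycodone while the device is in place could meet both conditions, and no rule says which prevails.

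**4. What the restriction does to the comparison.** Let pA and pS be the risks of an event in the active and sham arms, and rA and rS the probabilities that such an event is called related. Treat each participant as having at most one event.

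- All-event comparison: pA − pS.
- Device-related comparison, on the first reading in step 2: pA·rA − pS·rS.

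The documents give none of these four quantities. The values below are assumptions for illustration, with 20 per arm.

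- *Even attribution (rA = rS = r).* The difference becomes r × (pA − pS). With pA = 40% and pS = 20%, the all-event difference is 20 points (8 against 4 participants). With r = 0.9 it is 0.9 × 20 = 18 points; with r = 0.5 it is 0.5 × 20 = 10 points. If the excess lies wholly in event types always called unrelated (r = 0), none of it is seen.
- *Uneven attribution with equal risks (pA = pS = p).* The difference becomes p × (rA − rS). With p = 40%, rA = 0.9 and rS = 0.5 it is 0.40 × 0.40 = 16 points (7.2 against 4.0 expected of 20) with no true difference. For p from 20% to 60% it runs from 8 to 24 points; with 0.8 against 0.6 it runs from 4 to 12 points. If rA = rS it is zero.

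The loss under even attribution needs no bias at all. The spurious difference in the second case arises only if attribution differs by arm.

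**The case against.** The strongest case against has four parts.

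*Related is drawn broadly.* Timing alone suffices and 8.3.3.2 treats the study product as always suspect, so few events during the 7-day implant would be excluded. This stands in part. A reader might infer that new sensory change or weakness in the treated limb would go unseen; the documents do not support that, because such events would normally count as related and nerve injury is a listed risk. It does not cover events with an established alternative cause, which the same section calls Not Related.

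*Attribution should be even.* Active and sham generators look alike, and section 8.1 has masked observers perform all postoperative assessments. A reader might infer from the restriction that the comparison is biased between arms, and the documents do not show that. What remains is narrower. Section 6.1.1 masks investigators and clinical staff "with the only exception being the unmasked individuals who insert the RELAY and program the stimulator", and section 8.3.3.2 does not say that the clinician who grades relationship must be masked.

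*Nothing is lost.* All events are recorded, serious events go to the sponsor within 24 hours, an independent medical monitor reviews safety, and a table could be added at reporting. This is correct about the data and about oversight. It does not supply a prespecified comparison, and a table chosen after results are known carries less weight.

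*The trial is small and the comparison descriptive.* With 20 per arm, any safety comparison is imprecise. That applies equally to a table of all events, so it neither excuses the restriction nor measures its effect.

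**Conclusion.** The point holds as a gap in the analysis plan. Followed as written, section 9.4.4 gives no randomised comparison of all adverse events or all serious adverse events, and the subset it does compare is undefined and does not correspond to the category graded in 8.3.3.2.

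Its size cannot be stated: the share of events that would be called unrelated is not in the documents, and the figures in the working show only how the effect depends on it. The conclusion rests on two readings of the text: that the comparison sentence in 9.4.4 refers back to device-related events, and that no table of all events by arm is planned elsewhere. It does not rest on any assumption that attribution differs between arms.

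The primary efficacy analysis and the collection of safety data are unaffected. The change should be made before the randomised data are unblinded, since a main use of this trial is to prepare a pivotal study.

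**What to change.** In section 9.4.4:

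- Tabulate all adverse events and, separately, all serious adverse events by randomised arm in the modified intention-to-treat population of section 9.4.5. Give participants with at least one event as n/N, by severity and by relationship. Keep this descriptive; intervals for risk differences are optional.
- Keep device-related events as a subset and define the term, either as events graded Related under 8.3.3.2 or as a named list of event types.
- Show run-in participants separately. They were not randomised, all receive active stimulation, and some may also have a continuous local anesthetic infusion.
- Reconcile 9.4.4 with 8.3.4 on which events are recorded, and with 8.3.3.2 on the name of the category. In 8.3.3.2, say which condition prevails when timing and an alternative cause both apply, and state whether the clinician who grades relationship is masked.

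The cost is one extra table from data already collected and a few sentences of text. No new assessments and no change to sample size are needed.

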9.4.5 BASELINE DESCRIPTIVE STATISTICS

As described above, balance on baseline covariates will be assessed using absolute standardized difference (ASD). Variables considered imbalanced will be adjusted for in the statistical analyses. Analyses will be carried out using modified intention-to-treat i.e., participants who received any study treatment will be analyzed according to the group to which they were randomized.

9.4.6 PLANNED INTERIM ANALYSES

A futility analysis will be performed once 20 participants have been randomized and data through post-operative Day 7 are available. The following two criteria must be achieved to move forward: 1) RELAY deployment success in the lead/catheter insertion of $\geq 85\%$ in RELAY participants, and 2) a conditional power (Cp) of $\geq 30\%$ for the primary efficacy endpoint. Of note, a standardized effect size of 0.49 would not meet criteria to continue. There will be no stopping for early efficacy.

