4 STUDY DESIGN

4.1 OVERALL DESIGN

This is a single-center, sham-controlled study to investigate the efficacy and safety of RELAY use of a device that enables the delivery of both local anesthetic and neuromodulation (peripheral nerve stimulation) to treat postoperative pain.

Following a training run-in period, the randomized single blind sham-controlled part of the study will commence. The purpose of the training run-in period is to ensure that RELAY can be safely placed next to a target nerve, successfully programmed and induce peripheral nerve block and neuromodulation based on the instructions for use. This will ensure familiarity with the device prior to the randomized portion of the study. The training period will consist of up to 20 participants (~ 5 to 10 catheter lead insertions per anesthesiologist) across at least two different surgical procedures.

It is anticipated that during the training run-in phase, the successful deployment of the RELAY system will be achieved 80% or more of the time. If less than 80% is achieved, the study will not proceed to the randomized portion. A brief study report will be submitted to the FDA prior to initiating the randomized portion.

RELAY deployment success will be defined as a successfully placed catheter/lead as evidenced by sensory changes in the distribution of the target nerve with (1) electrical stimulation eliciting paresthesia and (2) inducing a conduction nerve block with injection of local anesthetic injection leading to either decreased or absent sensation to cold with alcohol swab.

The randomized portion will include 40 participants (with up to 10 additional participants to account for drop-outs) randomized (1:1) to the experimental and sham arms, respectively. A futility analysis will be performed once 20 participants have been randomized and data through post-operative Day 7 are available. The following two criteria must be achieved to move forward: 1) RELAY deployment success in the lead/catheter insertion of $\geq 85\%$ in RELAY participants, and 2) a conditional power (Cp) of $\geq 30\%$ for the primary efficacy endpoint. Of note, a standardized effect size of 0.49 would not meet criteria to continue. There will be no stopping for early efficacy.

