9.2 SAMPLE SIZE DETERMINATION

The sample size estimation is centered around the hypothesis that neuromodulation lowers the severity of pain the week after surgery. To this end, the primary outcome measure is the median "average" daily pain intensity for Days 1-7 as measured with the NRS within the BPI. This outcome measure was used by the authors previously for a similar study treating the same patient population with a different percutaneous peripheral nerve stimulation pulse generator and lead, and we therefore will use the resulting mean (SD) from each treatment group to power the present pilot study [Ilfeld et al. Anesthesiology 2021; 135: 95-110]. Specifically, the treated and sham groups reported a mean (SD) of 1.1 (1.1) and 3.1 (1.7), respectively. Assuming a standard deviation of 2.05, a sample size of 20 participants per group provides 85.2% power to detect a group difference of 2 points. With an additional 10 participants allowed to replace drop-outs in the randomized portion, a total of up to 70 participants may be enrolled in this study combining the run-in and randomized stages.

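### The 85.2% power in Section 9.2 ignores the two mandatory interim criteria in 9.4.6; the conditional-power rule alone lowers it to about 77% for the planned test

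*Combined protocol and SAP*

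**What the plan says.** Section 9.2 plans on an SD of 2.05 and states that 20 per group "provides 85.2% power to detect a group difference of 2 points". It does not mention an interim look. The 2-point difference comes from an earlier sham-controlled trial of another stimulator, with mean (SD) 1.1 (1.1) treated and 3.1 (1.7) sham.

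Section 9.4.2 makes the primary test an unadjusted Mann-Whitney U test at P<0.05, and 9.4.3 describes the tests as two-tailed.

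Section 9.4.6, with the same text in the synopsis and in 4.1, sets the interim: "A futility analysis will be performed once 20 participants have been randomized and data through post-operative Day 7 are available". It continues: "The following two criteria must be achieved to move forward". The first criterion is at least 85% for "RELAY deployment success in the lead/catheter insertion" in RELAY participants. The second is conditional power of at least 30% for the primary endpoint. The section adds "Of note, a standardized effect size of 0.49 would not meet criteria to continue" and rules out early stopping for efficacy. It gives no formula for conditional power and assumes no true deployment rate for the randomised part.

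Section 4.1 defines deployment success by sensory changes with "electrical stimulation eliciting paresthesia and (2) inducing a conduction nerve block". Section 6.1.1 has randomisation "stratified by anatomic location (shoulder and foot/ankle surgery) in a 1:1 ratio and in blocks of 2".

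**The concern.** A binding futility rule removes some trials that would have gone on to reject, and without an early efficacy stop nothing offsets that loss. The 85.2% is therefore the power of a trial that always runs to 40 participants, which is not the trial in 9.4.6. A reader of 9.2 takes the type II error to be about 15%, when the plan's own second criterion already makes it more than 20%.

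The deployment criterion adds a further chance of stopping at 20, and the plan does not describe its size. Two failed placements in the active arm would end the trial before the pain question is answered. Because the study is meant to prepare a pivotal trial, the sponsor and the regulator should see both risks.

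**Working it through.** **Inputs.** Difference 2, SD 2.05, 20 per group (9.2); two-sided 0.05 (9.4.2, 9.4.3); interim at 20 randomised, so about 10 per arm and information fraction t = 0.5 (9.4.6); 1:1 in blocks of 2 within two strata (6.1.1). If both strata hold an odd number at the interim, each can be off by one, so the active arm has 9 to 11 participants.

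**1. The stated power.** Two-sample t-test, noncentrality (2/2.05) × √(20/2) = 3.085, df 38: power 85.23%. This reproduces 85.2%, as a fixed design with no interim.

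**2. Which conditional power is meant.** With interim statistic z = d × √(10/2), where d is the observed standardised effect, conditional power under the current trend is

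CP = Φ{[z√t + (z/√t)(1 − t) − 1.96] / √(1 − t)}.

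At d = 0.49: z = 1.096, numerator 1.414 × 1.096 − 1.96 = −0.41, divided by 0.707 = −0.58, so CP = 28.1%. This fails the 30% criterion, as the protocol says. If the remaining data are instead assumed to follow the planning effect, d = 0.49 gives CP = 69% and the trial would continue. Of these two, only the current trend fits the protocol's remark.

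**3. Effect of that rule on power.** CP = 30% needs z = (1.960 − 0.5244 × 0.7071)/1.4142 = 1.124, that is d = 1.124/√5 = 0.503. At the planning effect, the probability of falling below it is Φ(1.124 − 0.9756 × √5) = Φ(−1.058) = 14.5%.

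Simulation with normal data at the planning effect (200,000 trials for the t-test, 40,000 of them for Mann-Whitney), with the interim criterion computed from the standardised mean difference:

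| Final test | No interim | After the conditional-power rule |
|---|---|---|
| t-test | 85.3% | 78.5% |
| Mann-Whitney (planned) | 83.1% | 76.8% |

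**4. The deployment criterion.** With n active participants the smallest count reaching 85% is 8 of 9 (88.9%), 9 of 10 (90%) or 10 of 11 (90.9%); 8 of 10 is 80% and fails. So at most one failure is allowed in each case, and P(stop) = 1 − [pⁿ + n pⁿ⁻¹(1 − p)]. For n = 10 and p = 0.90: 1 − (0.349 + 0.387) = 26.4%. The true rate p is an assumption throughout.

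| Assumed true success | 9 active | 10 active | 11 active |
|---|---|---|---|
| 80% | 56.4% | 62.4% | 67.8% |
| 85% | 40.1% | 45.6% | 50.8% |
| 90% | 22.5% | 26.4% | 30.3% |
| 95% | 7.1% | 8.6% | 10.2% |
| 98% | 1.3% | 1.6% | 2.0% |
| 99% | 0.3% | 0.4% | 0.5% |

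This table reads RELAY participants as the active arm. The definition of success needs paresthesia on stimulation, and under 6.1.1 no current reaches the electrodes in the sham arm. If all 20 insertions counted, 17 of 20 would be needed and a device at 90% would be stopped about 13% of the time.

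**The case against.** **The 85.2% is not a miscalculation.** Section 9.2 gives it as what 20 per group provides, and it reproduces exactly. This stands: the fault is an omission.

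**The planning SD may be cautious.** With the SDs of 1.1 and 1.7 quoted in 9.2, simulated power is 99.0% fixed and 97.0% after the conditional-power rule, so the loss would be small. This stands as a comment on size. But the plan chose 2.05 and its 85.2% depends on that choice, so the post-interim figure belongs on the same footing.

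**Deployment is a feasibility question.** Stopping when 2 of 10 placements fail is the rule working as written, and the randomised part follows a run-in meant to build familiarity with the device. At a true 98% or more the criterion costs less than 2 points of power. This also stands, and is why deployment is shown here as a range and kept apart from the power figure.

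**Stronger readings that the documents do not support.** A reader might multiply 0.736 (passing deployment at 90%) by 0.785 and conclude that real power is about 58%. That rests on a rate found nowhere in the plan, on independence of deployment and pain, and on a t-test that is not the planned analysis. A reader might also say that the 85% threshold is unusable because 85% of 10 cannot be observed. The rule is clear at any count, and writing it as a count changes no decision. Finally, Section 4.1 says of the run-in "If less than 80% is achieved, the study will not proceed to the randomized portion" without fixing the number at which the rate is read, and a reader might infer that it could be read at whichever count is favourable. No text permits repeated reading, and a report goes to the FDA before randomisation starts.

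**Conclusion.** The concern holds as an omission in the power statement. At the plan's own planning effect and SD, the conditional-power criterion takes power from 85% to about 78% by t-test. For the planned Mann-Whitney test the fall is from about 83% to about 77%. No deployment rate is needed for this. It does rest on the current-trend reading of conditional power and on normally distributed scores. Under the planning-effect reading the loss would be negligible (simulated t-test power 85.1%), but that reading contradicts the remark about 0.49.

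The deployment criterion adds a stopping risk that the plan does not disclose. Its size depends on the true success rate: about one in four at 90%, negligible at 98% or above. The documents do not support a single joint power figure.

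**What to change.** In 9.2, either replace 85.2% with the power of the planned Mann-Whitney test after the conditional-power rule (about 77% at 2 points and SD 2.05), or label 85.2% as fixed-sample t-test power and put the post-interim figure beside it. Say that conditional power is taken under the current trend.

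In 9.4.6, report the probability that the deployment criterion stops the trial over assumed true rates from 80% to 99%, labelled as assumptions, and state that RELAY participants means the active arm if that is the intent. If a joint power is also given, label it as assuming independence of deployment and pain. Adding the passing counts (8 of 9, 9 of 10, 10 of 11) is optional clarification.

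The cost is wording only. Neither criterion changes and no participants are added, but the stated power becomes less favourable.
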